2.7 Statistical Analysis and Sample Size Justification

The PI, [name], will be responsible for analyzing all study data. The blind will be held at the local site by the VAPAHCS research pharmacist. Once all data has been cleaned and locked, [name] will be unblinded to conduct the final analyses.

Variables/Time Points of Interest

Objective and subjective sleep variables (total sleep time, sleep efficiency, wake after sleep onset, sleep quality) will be collected continuously during the 2-week baseline and the three-week intervention. Subjective alertness assessment will also be collected continuously over the five-week protocol. All of these will be used in the study analyses.

Statistical Methods

The purpose of this study is to test the hypothesis that ingestion of 10 mg of suvorexant 30 minutes prior to daytime sleep initiation in individuals working overnight shifts will significantly improve both objective (total sleep time, sleep efficiency, wake after sleep onset) and subjective (sleep quality) measures of sleep. A secondary goal is to test the hypothesis that ingestion of 10 mg of suvorexant 30 minutes prior to daytime sleep initiation will (1) increase subjective measures of alertness during the night shift and (2) decrease total sleep time during nocturnal sleep episodes on off-days. To accommodate the nested nature of the data (days nested within persons), analyses will be conducted in a multilevel modeling framework (19). Specifically, the total sleep time (TST), as an example, will be modeled as: $TST_{it} = \gamma_{00} + \gamma_{01} * group_i + u_{0i} + e_{it}$, where the TST obtained above for person i on day t , TST_{it} , are modeled separately as a function of between-person and within-person differences. Specifically, γ_{00} , indicates the expected TST score for a prototypical participant on a prototypical day (the reference category); γ_{01} captures between-group differences in sleep (placebo group vs. drug group); and u_{0i} and e_{it} capture additional between-person and occasion-specific differences not otherwise explained. All models will be fit using SAS 9.4 (proc mixed) with restricted maximum likelihood estimation. Effect size will be evaluated with respect to proportional reduction in unexplained variance from an informative baseline model (*pseudo-R²*, see (19)).

Exploratory measures:

While the primary measures in this study will examine *prospective* changes in sleep, we will also collect data that will

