examine *retrospective* changes in sleep. These include examining changes in subjective measures of sleep quality that are captured in the BSWSQ, ISI, and FOSQ-10 questionnaires. Changes on these questionnaires will be examined with repeated measure ANOVA. Another exploratory measure to be analyzed in the same manner will be a change in depressive symptom severity as captured on the CES-D. A final exploratory measure will be to examine the change in the number of caffeinated beverages during work shifts. Given that there is tremendous variability in the caffeine content of caffeinated beverages, within subject changes will be examined with multilevel modeling.

Power/Sample Size:

For estimation of sample size, we have reduced our aim to the single, most important outcome measure - will sleep efficiency improve in the drug condition - and reduced the statistical testing to a *t*-test. In previously published work (20), a variance of 3.62% - 3.87% was observed following use of 10 mg of suvorexant or placebo. For purposes of this sample size estimation, we can estimate $\sigma = 5.55\%$ (average variance * 150%, with the increase due to our use of actigraphy instead of polysomnography as a reporter). Setting $\alpha = 0.05$ and power = 80%, we would be able to detect a difference of 5.2% in sleep efficiency (i.e., that which was observed in a previous trial of 10 mg suvorexant in those with insomnia (21)) with 19 participants in each group (n=38 total).

**PROTOCOL
 APPLICATION FORM
 Human Subjects Research
 Stanford University**

Title : A double-blind, placebo-controlled, randomized, parallel design study to examine the effectiveness of 10 mg suvorexant in improving daytime sleep in shift workers

Approval Period: Draft

Protocol Director				
Name [name]		Degree (Program/year if student) PhD		Position, e.g. Assistant Professor, Resident, etc. Asst Professor
Department Psych/Sleep Medicine	Mail Code 5550	Phone [REDACTED]	Fax	E-mail [contact]
CITI Training current				Y

Admin Contact				
Name [name]		Degree (Program/year if student) BS		Position, e.g. Assistant Professor, Resident, etc.
Department Psychiatry and Behavioral Sciences	Mail Code 5550	Phone [REDACTED]	Fax	E-mail [contact]
CITI Training current				Y

Investigator				
Name		Degree (Program/year if student)		Position, e.g. Assistant Professor, Resident, etc.
Department	Mail Code	Phone	Fax	E-mail
CITI Training current				

Other Contact				

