After conclusion of the study, participants would be able to contact their physicians to obtain a prescription for the medication used in this study.

- g) Study Endpoint. What are the guidelines or end points by which you can evaluate the different treatments (i.e. study drug, device, procedure) during the study? If one proves to be clearly more effective than another (or others) during the course of a study, will the study be terminated before the projected total participant population has been enrolled? When will the study end if no important differences are detected?**

The primary endpoint of this study is a change in total sleep time during day time sleep episodes. Given the blinding of the study and the relatively small population being studied, we do not intend to examine the primary outcome prior to study completion (38 total subjects).

3. Background

- a) Describe past experimental and/or clinical findings leading to the formulation of the study.**

The hypocretins (orexins) are a pair of neuropeptides produced by a small group of hypothalamic neurons

Title : A double-blind, placebo-controlled, randomized, parallel design study to examine the effectiveness of 10 mg suvorexant in improving daytime sleep in shift workers
Approval Period: Draft

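### Section 2.7's model has no baseline term although the primary endpoint is a change; extending it to daily rows from both phases with only a person intercept would understate the standard error

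*Combined protocol and SAP*

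**What the plan says.** - **Model.** Section 2.7, Statistical Methods, treats days as nested within persons and gives one equation, for total sleep time as an example: an intercept γ00, a group coefficient γ01, a person term u0i and a day term eit. The last two "capture additional between-person and occasion-specific differences not otherwise explained". γ01 is described as the placebo-versus-drug difference. Fitting is by PROC MIXED with REML. There is no phase, group-by-phase or baseline term, and no residual covariance or degrees-of-freedom method is stated.
- **Endpoint.** Section 2g of the application form: "The primary endpoint of this study is a change in total sleep time during day time sleep episodes". Section 2.7, under Exploratory measures, likewise describes the primary measures as looking at prospective changes in sleep.
- **Data.** Section 2.7, Variables/Time Points of Interest, covers the two baseline weeks and the three intervention weeks and adds: "All of these will be used in the study analyses". It does not say how the baseline enters.
- **Caffeine.** For this exploratory outcome, "within subject changes will be examined with multilevel modeling"; no random-effects structure is given.

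**The concern.** The declared endpoint is a change, but the only printed model contains nothing that represents one. The analyst must bridge that gap, and the plan does not say how.

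One direct bridge within the stated framework is to stack baseline and treatment days as outcome rows and test group-by-phase. In that contrast the person intercept cancels. If it is the only random effect, the model assumes that everyone's true change is the same within an arm. People will plausibly differ in how their sleep shifts between phases, and that variation would be almost entirely missing from the standard error. At stake is the type I error of the primary comparison, should the model be extended in this way.

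**Working it through.** **1. The plan's own figure.** Section 2.7 states "we would be able to detect a difference of 5.2% in sleep efficiency" with 19 per group, SD 5.55, α 0.05 and 80% power. The normal formula gives 2 × (1.96 + 0.8416)² × (5.55/5.2)² = 17.9, so 18 per group. The exact two-sided t-test has power 78.0% at 18 and 80.2% at 19, so 19 reproduces. That calculation uses one value per person, so the choice of random effects does not alter it.

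**2. Inputs.**
- n = 19 per arm (section 2.7).
- b = 8 baseline and t = 12 treatment daytime sleeps: four nights a week (section 8h, inclusion criteria) over 2 and 3 weeks, assuming one daytime sleep per shift.
- σ, the day-to-day SD, and τ, the between-person SD of true change, are not in the documents. Only τ/σ matters; the assumed range is 0 to 1.
- Residuals are independent (assumed; varied in step 5).

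**3. The printed model.** γ01 is tested against between-person variance. In null simulations (4,000 trials per setting) it rejected in 4.1% to 5.9%, whether fitted to treatment weeks or to all five weeks. Pooling all weeks has a different cost. A drug effect δ is present only on treatment days, so γ01 estimates 12/(8 + 12) × δ = 0.6δ.

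**4. Group-by-phase with a person intercept only.** Set σ = 1.
- True variance of the difference in mean change: (2/19) × T, where T = τ² + 1/8 + 1/12 = τ² + 0.2083.
- Variance the model reports: (2/19) × M, where M = 0.2083 × [1 + τ² × (8 × 12/20) × 36/720] = 0.2083 × (1 + 0.24τ²). Here 36 = 38 − 2 and the residual degrees of freedom are 760 − 38 − 2 = 720. The residual therefore absorbs a small part of the variation in change.
- SE ratio = √(T/M); type I error = 2Φ(−1.96/ratio).

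| τ/σ | T | M | True SE / model SE | Type I, formula | Type I, simulated |
|---|---|---|---|---|---|
| 0 | 0.2083 | 0.2083 | 1.00 | 5.0% | 4.6% |
| 0.25 | 0.2708 | 0.2115 | 1.13 | 8.3% | 8.0% |
| 0.5 | 0.4583 | 0.2208 | 1.44 | 17.4% | 17.1% |
| 0.75 | 0.7708 | 0.2365 | 1.81 | 27.8% | 27.9% |
| 1.0 | 1.2083 | 0.2583 | 2.16 | 36.5% | 36.4% |

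In minutes, with an assumed σ of 60 and τ of 30, the true SE is 60 × √(2/19 × 0.4583) = 13.2, while the model reports 60 × √(2/19 × 0.2208) = 9.1.

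**5. Sensitivity.** With 10 and 15 days the simulated range is 4.9% to 40.8%. With day-to-day autocorrelation of 0.3 and 8 and 12 days it is 13.8% (at τ = 0) to 37.9%. Comparing one change score per person, which in balanced data corresponds to adding a random person-by-phase effect, gave 4.3% to 5.3% in every setting.

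**The case against.** A reader might infer that the trial's planned p-values are too favourable, or that type I error for the primary endpoint exceeds 5%. The documents do not support that. The inflated test appears nowhere in the plan: the printed equation has no phase or group-by-phase term, and its group test holds its level. Saying that baseline data will be used is just as compatible with a baseline covariate or a per-person change score. Either of these tests group against between-person variance and causes no inflation. Nor can every multilevel analysis be assumed to be intercept-only, since the equation is offered as an example and the caffeine model's random structure is not given.

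Two further points are fair. Randomisation makes the arms equal at baseline in expectation, so a treatment-weeks difference in level is a valid estimate of the drug effect. And the size of any inflation rests on an assumed τ/σ; at zero, with independent days, there is none.

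All of this stands, and it makes the type I error concern conditional. It does not close the gap: the printed coefficient is not a change, the printed model makes no use of two weeks of baseline recordings except by pooling them, and nothing rules out the faulty extension.

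**Conclusion.** The point holds in conditional form. As written, the model is valid for comparing levels but does not match the declared change endpoint. It either ignores the baseline or, if all five weeks are pooled, shrinks the effect to about 0.6 of its size with 8 and 12 days. If change is tested as group-by-phase on daily rows with only a person intercept, type I error runs from about 5% to 36% for τ/σ from 0 to 1. Those figures assume 19 per arm, 8 and 12 days and independent residuals. The documents do not fix τ/σ, so no single value in that range can be claimed.

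**What to change.** In section 2.7, state that the primary analysis uses treatment-phase daytime sleeps only, with group and the person's own baseline mean as fixed effects and a random person intercept. With that covariate, the group coefficient is the same whether the outcome is the level or the change from baseline, so it serves the endpoint in section 2g.

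If daily rows from both phases are modelled instead, including for the exploratory caffeine change, specify fixed phase and group-by-phase terms and a random person-by-phase effect as well as the intercept, and name group-by-phase as the test of change. Adding the random effect without those fixed terms would still leave no coefficient for change. The two approaches are different models, so the plan should name one as primary.

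Baseline adjustment is a free improvement; the random phase effect is a cheap one. The cost is one extra model term and, for the second option, wider intervals than an intercept-only change model would print. No new data are needed and n=38 is unchanged.

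### Pseudo-R² is the only effect size named and no confidence interval is planned for the drug–placebo difference, so the stated effect size cannot be read against the 5.2-point planning difference

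*Combined protocol and SAP*

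**What the plan says.** The Statistical Methods part of section 2.7 gives a random-intercept model, with total sleep time as the example: outcome for person i on day t = γ00 + γ01·group_i + u_0i + e_it. Group is the only predictor and carries only the person subscript. The coefficient γ01 "captures between-group differences in sleep (placebo group vs. drug group"), so it is in the outcome's own units. On fitting, the plan says: "All models will be fit using SAS 9.4 (proc mixed) with restricted maximum likelihood estimation".

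One sentence deals with effect size: "Effect size will be evaluated with respect to proportional reduction in unexplained variance from an informative baseline model". It labels the quantity pseudo-R² and cites reference 19. It does not say whether the unexplained variance is within-person, between-person or total, and it does not specify the baseline model. No confidence interval for γ01 appears in the available text.

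The Power/Sample Size part works on a different scale. With σ = 5.55%, α = 0.05, 80% power and 19 per group, "we would be able to detect a difference of 5.2% in sleep efficiency". Section 2(g) of the protocol application names change in daytime total sleep time as the primary endpoint.

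**The concern.** The trial is sized on a difference in percentage points, but the effect size it plans to report is a proportion of variance. That proportion has three weaknesses here.

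- **No direction or units.** The effect enters as a square, so a benefit and a harm of equal size give the same value.
- **Not fixed by this text.** A predictor that is constant within person can reduce the variance of u_0i but not that of e_it, so the answer depends on which component is used. Section 2.7 has the principal investigator unblinded to run the final analyses. If the choice is not fixed in advance, it would be made with treatment codes known.
- **Imprecise at 38 people**, as shown in the working.

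In a trial this small, much of the value lies in saying which differences the data support and which they exclude. That takes the difference and its interval.

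**Working it through.** **Inputs from section 2.7:** difference 5.2 points, SD 5.55 points, 19 per group, α = 0.05, power 80%. **Assumed:** 12 daytime sleeps per person in the intervention (four nights a week from the inclusion criteria × 3 weeks); nightly residual SD of 8 or 10 points, or intraclass correlation (ICC) of 0.2 to 0.7. The documents give neither the residual SD nor the ICC.

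**1. The plan's own figure.** Two-sided two-sample t-test: noncentrality = 5.2 / (5.55 × √(2/19)) = 5.2 / 1.80 = 2.89 on 36 df. Power is 80.2% with 19 per group and 78.0% with 18, so 19 per group reproduces.

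**2. Pseudo-R² in closed form, taking 5.55 as the between-person SD.**
- Variance explained by a 1:1 group variable = (5.2/2)² = 6.76.
- Between-person variance = 5.55² = 30.80.
- On between-person variance: 6.76 / (6.76 + 30.80) = 0.18.
- On total variance, residual SD 8: 6.76 / (6.76 + 30.80 + 64) = 0.067.
- On total variance, residual SD 10: 6.76 / (6.76 + 30.80 + 100) = 0.049.
- On the residual: 0, because group does not vary within a person.

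**3. Simulation of the written model, taking 5.55 as the SD of person means.** REML for balanced data, true effect 5.2 points, 19 per group, 12 days each, 4,000 runs per setting. Entries are means.

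| Assumed ICC | Residual pseudo-R² | Between-person pseudo-R² | Total pseudo-R² | γ01 estimate |
|---|---|---|---|---|
| 0.2 | 0.000 | 0.22 | 0.06 | 5.2 |
| 0.35 | 0.000 | 0.20 | 0.08 | 5.2 |
| 0.5 | 0.000 | 0.19 | 0.11 | 5.2 |
| 0.7 | 0.000 | 0.18 | 0.13 | 5.2 |

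At ICC 0.5 the central 95% range of the between-person value was about 0.00 to 0.44, and about 3% of runs were negative despite a real effect. With unequal numbers of days per person the residual value would be near zero rather than exactly zero.

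**4. Interval for the difference in sleep efficiency.** Half-width = t(0.975, 36) × SD of person means × √(2/19), with t = 2.028.
- If 5.55 is the SD of person means: 2.028 × 5.55 × 0.3244 = 3.65 points.
- If 5.55 is the between-person SD and residual SD is 8: person-mean SD = √(30.80 + 64/12) = 6.01, half-width 3.95.
- The same with residual SD 10: √(30.80 + 100/12) = 6.26, half-width 4.12.

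**5. What the interval adds.** With a half-width of 3.65, an estimate below 5.2 − 3.65 = 1.55 points excludes 5.2, and one above 3.65 excludes zero. An estimate between those values excludes neither. Pseudo-R² cannot make these distinctions.

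**The case against.** The strongest reply is that the plan already estimates the drug effect. γ01 is defined in the same paragraph as the group difference, in outcome units and with a sign, and pseudo-R² is named alongside it. That stands. A reader might infer that the trial cannot express its drug effect in minutes or points, or cannot judge the 5.2-point target at all. The documents do not support that: the limitation belongs to the named metric, and the fitted model yields the estimate. What is missing is a statement that this estimate, with an interval, is the reported effect size.

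A reader might also infer that the planned pseudo-R² will be near zero however well the drug works. The plan never says the residual will be used, and on the between-person component the value is about 0.18–0.22. Nor is zero a general result for a treatment assigned to persons. The equation is offered as an example, and baseline data are also to be used. Adding 8 assumed baseline sleeps and a group-by-period term would give a within-person value of about 0.02, 0.06 and 0.12 at ICC 0.2, 0.5 and 0.7.

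Reference 19 may fix the component and the comparison model. It is not available here, so the claim is only that this text does not state them.

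Two further points limit the remedy. The 5.2-point figure is for sleep efficiency and gives no benchmark for total sleep time. And the written model has no period term: if all 35 days entered it, γ01 would mix treated and untreated days, and a 5.2-point effect would shrink to 21/35 × 5.2 = 3.1 points if days count equally. Naming γ01 without defining the window could lock in a diluted estimate.

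**Conclusion.** The point holds as a mismatch between the effect size the plan names and the quantity the trial was sized to detect. A single true 5.2-point effect can appear as 0, about 0.05–0.13 or about 0.18–0.22, depending on a component this text leaves unstated, and none of these can be set against 5.2 points. The residual zero follows from the written model. The other ranges rest on the assumed ICC or residual SD, and the simulated values also on 12 balanced sleeps per person. The ±3.7 and ±4 half-widths depend on which SD 5.55 represents.

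This is worth changing because it affects what a 38-person trial can say about effects supported or excluded. It does not invalidate the analysis: no test, α, power or sample-size figure changes.

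**What to change.** Replace the effect-size sentence in section 2.7 with wording such as: *The effect size is the model-estimated drug–placebo difference during the three-week intervention period, in the outcome's own units (minutes for total sleep time, percentage points for sleep efficiency), with its 95% confidence interval. For sleep efficiency only, it will be read against the 5.2-point planning difference.*

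State in the model description that untreated baseline days are not averaged into this difference. If pseudo-R² is kept, call it a descriptive supplement and name its variance component and comparison model.

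The cost is a few lines of SAP text, settled before unblinding. No new data are needed, and the estimate and its interval come from the same kind of mixed-model fit. The one real decision is how the analysis window is written into the model.

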Baseline visit (3 hours): Consent process followed by baseline assessments using questionnaires, blood draw, urinalysis, electrocardiogram, and physical exam

Week 1-2: Sleep will be monitored with a wrist-worn device that monitors movement as well as participant-completed logs. No changes in behavior.

Weeks 3-5: Sleep will be continued to monitored as during baseline. Subjects will also take a pill 30 minutes prior to day time sleep attempts. This pill will have either drug or placebo (randomized)

End of study visit (2 hour): Same procedures as baseline visit.

- b) Explain how the above research procedures are the least risky that can be performed consistent with sound research design.**

All procedures in this study were designed with the goal of minimizing exposure to risk balanced with gaining a greater understanding of whether this treatment would help the individuals who participate in this study and for whom there is no currently available FDA-approved therapy.

- c) State if deception will be used. If so, provide the rationale and describe debriefing procedures. Since you will not be fully informing the participant in your consent process and form, complete an alteration of consent (in section 13). Submit a debriefing script (in section 16).**

Deception will not be used.

- d) State if audio or video recording will occur. Describe what will become of the recording after use, e.g., shown at scientific meetings, erased. Describe the final disposition of the recordings.**

Audio and video recordings will not occur.

- e) Describe alternative procedures or courses of treatment, if any, that might be advantageous to the participant. Describe potential risks and benefits associated with these. Any standard treatment that is being withheld must be disclosed in the consent process and form. (i.e. standard-of-care drug, different interventional procedure, no procedure or treatment, palliative care, other research studies).**

Instead of participating, individuals who work night shifts can use any one of a number of behaviors or medications to help them sleep during the day time. None of the available pharmacotherapies induce natural sleep and the behavioral therapies have efficacy in only a subset of individuals.

- f) Will it be possible to continue the more (most) appropriate therapy for the participant(s) after the conclusion of the study?**

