The risks of the Radioisotopes/radiation-producing machines (e.g., X-rays, CT scans, fluoroscopy) and associated risks.

None

The risks of the Physical well-being.

The wrist worn activity monitors may cause a rash (contact dermatitis) on the wrist underneath where the device makes contact with the skin. This risk is similar to wearing a wrist watch. If this occurs, we will recommend that participants move the watch and use skin cream on the rash.

The risks of the Psychological well-being.

There is a possibility of increased depressive symptoms following use of this medication. We will monitor this at the end of the first week of drug use. There is always a risk when completing questionnaires that participants will learn something about themselves that negatively affects their psychological well-being.

The risks of the Economic well-being.

Title : A double-blind, placebo-controlled, randomized, parallel design study to examine the effectiveness of 10 mg suvorexant in improving daytime sleep in shift workers

Approval Period: Draft

There is no likely risk to economic well-being.

The risks of the Social well-being.

There is no likely risk to social well-being.

Overall evaluation of Risk.

Low - innocuous procedures such as phlebotomy, urine or stool collection, no therapeutic agent, or safe therapeutic agent such as the use of an FDA approved drug or device.

- b) If you are conducting international research, describe the qualifications/preparations that enable you to both estimate and minimize risks to participants. Provide an explanation as to why the research must be completed at this location and complete the [LINKFORINTERNATIONALRESEARCHFORM] International Research Form. If not applicable, enter N/A.**

n/a

- c) Describe the planned procedures for protecting against and minimizing all potential risks. Include the means for monitoring to detect hazards to the participant (and/or to a potential fetus if applicable). Include steps to minimize risks to the confidentiality of identifiable information.**

Two weeks after initiating the baseline portion of the study, participants will return to the lab and be monitored for risk exposure. One week after initiating medication, subjects will again return to the lab and be monitored for risk exposure.

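### The exploratory questionnaire outcomes would be estimated more precisely by baseline-adjusted ANCOVA than by the planned repeated-measures ANOVA, whose treatment contrast is not named

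*Combined protocol and SAP*

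**What the plan says.** Section 2.7, under the label "Exploratory measures", assigns the BSWSQ, ISI and FOSQ-10 to one method: "Changes on these questionnaires will be examined with repeated measure ANOVA". It then adds: "Another exploratory measure to be analyzed in the same manner will be a change in depressive symptom severity as captured on the CES-D". It does not say whether the group effect, the time effect or their interaction is the drug-placebo test, and it mentions no baseline-adjusted analysis for these instruments.

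The visit schedule is in the application form, Study Procedures (item 2a). The baseline visit includes "baseline assessments using questionnaires", and the closing visit is described as follows: "End of study visit (2 hour): Same procedures as baseline visit". Each completer should therefore have at least one score before study drug and one after it.

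The risk section (item 9a) says of depressive symptoms: "We will monitor this at the end of the first week of drug use". It does not name the instrument used at that visit.

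The only sample-size statement in 2.7 concerns another outcome: "power = 80%, we would be able to detect a difference of 5.2% in sleep efficiency", with 19 participants per group. No effect size, SD, correlation or power is given for any questionnaire.

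**The concern.** A repeated-measures ANOVA with two arms and two visits produces three tests, and only the group-by-time interaction estimates the treatment effect in full. The time effect pools drug and placebo. The group main effect averages a score taken before treatment with one taken after it, so it estimates half the treatment effect. Section 2.7 leaves the choice open.

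Even with the right test chosen, the method gives up precision. The interaction is algebraically the t-test on change scores, which fixes the coefficient on baseline at 1. ANCOVA estimates that coefficient and, unless the two scores are very highly correlated, leaves less residual variance.

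At stake is the width of the intervals for the retrospective sleep questionnaires and the CES-D in a trial of 38 completers. The primary and secondary analyses are not affected.

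**Working it through.** **The plan's own figure.** Inputs from 2.7: difference 5.2, SD 5.55, alpha 0.05 (two-sided assumed, since sidedness is not stated), power 80%. The normal approximation gives 2 × (1.960 + 0.842)² × 5.55² / 5.2² = 17.9, so 18 per group. The exact t-test gives 18.9, so 19 per group, with power 80.2% at 19. The stated 19 is reproduced. It concerns sleep efficiency, and nothing below alters it.

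**Inputs for the questionnaires.** From the documents: 19 per group (N = 38) and scores at baseline and end of study. Assumed, because the documents give no values: baseline-to-follow-up correlation ρ from 0.3 to 0.8, equal SD at both visits (set to 1), a true drug-placebo difference of 0.8 SD, and a two-sided 5% test.

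**Formulas.**
- Group-by-time test (change scores): variance of the difference = 2(1 − ρ) × 2/19, on 36 df.
- ANCOVA: variance = (1 − ρ²) × 2/19 × (1 + 1/34), on 35 df. The factor 1 + 1/(N − 4) = 35/34 allows for estimating the baseline slope when the arms differ by chance at baseline.
- Ratio, ANCOVA to change score: (1 + ρ)/2 in large samples, and (1 + ρ)/2 × 35/34 here.

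**Results at 19 per group.**

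| ρ | SE, change score | SE, ANCOVA | Variance ratio | Variance cut | Power at 0.8 SD, change score | Power at 0.8 SD, ANCOVA |
|---|---|---|---|---|---|---|
| 0.3 | 0.384 | 0.314 | 0.669 | 33% | 53% | 70% |
| 0.5 | 0.324 | 0.285 | 0.772 | 23% | 67% | 78% |
| 0.7 | 0.251 | 0.235 | 0.875 | 12.5% | 87% | 91% |
| 0.8 | 0.205 | 0.197 | 0.926 | 7% | 97% | 98% |

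Power comes from the noncentral t distribution with noncentrality 0.8/SE. At ρ = 0.5, for example, this is 0.8/0.324 = 2.47 against 0.8/0.285 = 2.81. A simulation of 20,000 trials at each of ρ = 0.3, 0.5 and 0.7 gave variance ratios of 0.670, 0.773 and 0.873, in agreement with the table.

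**Where the advantage ends.** Setting (1 + ρ)/2 × 35/34 = 1 gives ρ = 2 × 34/35 − 1 = 0.943. Above about 0.94, ANCOVA is no longer more precise at this sample size.

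**If the group main effect were taken as the treatment test.** It estimates 0.4 SD when the true difference is 0.8 SD, with variance (1 + ρ)/2 × 2/19. At ρ = 0.5 the SE is 0.281, the noncentrality 0.4/0.281 = 1.42 and the power about 28%. At ρ = 0.7 the SE is 0.299, the noncentrality 1.34 and the power about 26%.

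**The case against.** The best defence is that this is a preference between two valid methods for outcomes that carry no confirmatory weight. Much of that stands. The questionnaires are labelled exploratory, no power claim is attached to them, and subjective sleep quality and alertness are analysed separately in the multilevel model. The size of the gain depends on ρ and on an effect size that the documents do not supply, and at ρ = 0.8 the gain is slight.

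Four stronger readings are tempting, and the documents do not support them.

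- *The plan throws away the baseline scores, or the analysis is biased.* It does neither. Baseline enters as the first repeated measure, and under randomisation the group-by-time test is unbiased.
- *Chance baseline imbalance is a further harm on top of the lost precision.* It is the same imprecision, already counted in the comparison of 2(1 − ρ) with 1 − ρ².
- *The plan intends a pooled time effect or a group main effect as the treatment test.* The text says neither. The trial is randomised and parallel, and 2.7 defines the treatment effect in its main model as placebo against drug, so the interaction is the natural reading. The gap is that the test is not named.
- *Detection of depressive symptoms depends on this ANOVA.* The risk section relies on monitoring after the first drug week, and nothing links that to this group comparison. If the CES-D is the instrument used then, it has a third time point and the two-visit algebra does not apply to it as it stands.

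The defence does not answer two points: the more precise analysis uses data already collected, and the sentence in 2.7 leaves the drug-placebo contrast unstated.

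**Conclusion.** The point holds as a modest one. For the four exploratory questionnaires the planned method is valid if the interaction is the test, but it is less precise than baseline-adjusted ANCOVA for any ρ below about 0.94. The cut in variance is about 33% at ρ = 0.3, falling to about 7% at ρ = 0.8. These figures assume two visits, equal SDs and 19 completers per group. The power figures also assume a 0.8 SD difference. Because ρ is not in the documents, the range is the finding, and no single value in it should be quoted as the gain.

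The sample size, the primary analysis and the secondary hypotheses are unchanged. Severity is low because the outcomes are exploratory.

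**What to change.** In the exploratory part of 2.7, replace the repeated-measures ANOVA with this rule: the end-of-study score on each of the BSWSQ, ISI, FOSQ-10 and CES-D is analysed by ANCOVA with group and the same instrument's baseline score, and the adjusted drug-placebo difference is reported with its 95% CI as the treatment comparison. If an instrument also has an on-treatment score before the final visit, use a mixed model for the post-baseline scores with baseline as covariate, so that participants who miss the last visit still contribute.

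If the repeated-measures ANOVA is kept, 2.7 should at least name the group-by-time interaction as the treatment test.

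The cost is SAP wording and one degree of freedom. No new data, visits or participants are needed.
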